1.2 Detailed Description

The Intervention Protocol of this research used part of the research protocol of Chinese scholar Du Min (Du, 2020). This research utilized augmentative training as an intervention, with the dependent variables being the subject's lower limb explosive power and Latin dance skill performance. Through extensive literature review, countermovement jumps, standing long jump, and 20m-sprint were identified as measures of lower limb explosive power(Chen et al., 2023). The experimental and control groups will be tested on the same Cha Cha Dance Gold Medal solo routine and recorded with a video camera. Score athletic performance according to 'the Latin Dance Technical Quality Elements of the World DanceSport Federation (WDSF) 2.1 Evaluation System'. Lower limb explosive power is closely related to the skill performance of cha-cha dance, and the review of the relevant literature was

determined to be posture, balance, footwork, preparation-movement-reduction, spinning and rotation, dynamic performance, and line extension as the test indicators of elementary skill (pei, 2023). In order to make the experiment more rigorous and scientific , to reduce the interference of uncontrollable factors , this research is Cluster Randomized Controlled Trial (CRCT) design , the students come from different areas . This experiment lasted for 8 weeks, 1.5 hours each time (Du, 2020), including one hour of physical fitness training and half an hour of specialized technical training. The sample was a population of university students who had been studying Latin dance for one year as well as more than one year, from Guangxi Normal University (Guilin) and Guilin University of Electronic Technology (Beihai), a total of 48 people. Dancers were randomly assigned to two different training locations and divided into experimental and control groups. Both groups will be trained in the Cha Cha Dance Single Gold Medal Moves. The experimental group will undergo plyometric training and the control group will undergo general training. This study measured the dependent variable three times throughout the intervention: baseline before the experimental intervention, post-test 1 after 4 weeks, and post-test 2 after 8 weeks. Finally, statistical analysis was conducted on the three test results.

2 Protocol Design

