Countermovement jumps: experimenters test using either arm swing or crossed hips (without any arm swing) while performing vertical longitudinal jumps on a smart jumping mat. The experimenter in this research uses a cross-legged waist when performing both the pre-test and post-test. The Smart Jump Pad in this research has been performed to measure the performance of the CMJ by providing signals from the platform in an iPad 7,5 IOS 12.1.1). When the test equipment is ready, under the direction of the test administrator, the experimenter stands on the Smart Jump Mat and performs a vertical longitudinal jump. The experimenter jumps to the best of their ability and each jump was automatically recorded on the iPad. Each participant jumped three times, and the best jump results are selected for data analysis in this research.(Meszler et al., 2019)

.

Standing long jumps: Measure the distance of the standing long jump with a measuring tape.

Participants stand slightly apart in front of the jump line, bend their knees, and move their arms backwards, then swing their arms and jump as far as possible; Stand on both feet while maintaining an upright position; Conduct two tests. Record the best score from two tests with an accuracy of 1 centimeter (Ambrozy et al., 2022).

20m-sprint : Use a stopwatch to record the duration of the participants' 30 m sprint.

Set cones at 0 and 20 meters along a straight line. Participants place their toes on the starting line or behind the starting line, start from a stationary position, and sprint at maximum speed over the cone at a distance of 20 meters before safely slowing down (Fischetti et al., 2018).

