Dynamic performance	Precise use and maximization of power generation in dance movements.	Precise use of power in dance movements	Precise application of power in most dance movements
Line extension	Maintains the lines and extensions of all body parts in both static and dynamic situations.	Maintains most body lines and extensions in both static and dynamic situations.	Maintains a portion of the body line and extends the line in both static and dynamic situations.

Table 6 Outcome Measurement Information

Test Name	Outcome Measure	Measure Method	Instrument	Unit	Suggestions
Explosive power	Countermovement jumps	Recorded maximum altitude	Smart jump mats, iPad	Centimeters (cm)	
	Standing long jumps	Measure the distance of the standing long jump with a measuring tape.	Measuring tape	Centimeters (cm)	
	20m-sprint	Use a stopwatch to record the duration of the participants' 20 m sprint.	Stopwatch	Seconds	
Posture	6 Experts	Recording cha-cha-cha solo gold medal moves, expert scoring	M120 high-speed camera	scores	
Balance	6 Experts	Recording cha-cha-cha solo gold medal moves, expert scoring	M120 high-speed camera	scores	
Footwork	6 Experts	Recording cha-cha-cha solo gold medal moves, expert scoring	M120 high-speed camera	scores	
Preparation-movement-reduction	6 Experts	Recording cha-cha-cha solo gold medal moves, expert scoring	M120 high-speed camera	scores	
Spinning and rotation	6 Experts	Recording cha-cha-cha solo gold medal moves, expert scoring	M120 high-speed camera	scores	
Dynamic performance	6 Experts	Recording cha-cha-cha solo gold medal moves, expert scoring	M120 high-speed camera	scores	
Line extension	6 Experts	Recording cha-cha-cha solo gold medal moves, expert scoring	M120 high-speed camera	scores	

5 Questionnaire information

This questionnaire adopts a 5-point Likert scale, with 1-5 representing increasing support (1=strongly disagree; 2=disagree; 3=not necessarily; 4=agree; 5=strongly agree). Please score the intervention program. If there is other content, you can add them and indicate the name. After reading the questionnaire, please rate the following aspects and tick "√" on the corresponding rating scale.

Table 7 Expert Evaluation Form for Outcome Measurement

6 References

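### Does the 20 m sprint need a fixed number of attempts, a scoring rule and a corrected distance before it can serve as an outcome?

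*Protocol*

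**What the plan says.** Protocol section 4.1 describes three tests of lower limb explosive power.

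- Countermovement jump: "Each participant jumped three times, and the best jump results are selected for data analysis in this research".
- Standing long jump: "Conduct two tests. Record the best score from two tests with an accuracy of 1 centimeter".
- Sprint: the timing sentence is "Use a stopwatch to record the duration of the participants' 30 m sprint". The next sentence sets the course: "Set cones at 0 and 20 meters along a straight line". The dancer starts from rest at or behind the line and runs at full speed past the far cone. No number of runs, rule for the analysed time or reading precision is given.

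Table 6 repeats the timing sentence with the other distance, "Use a stopwatch to record the duration of the participants' 20 m sprint", and adds a stopwatch and seconds. Section 1.2 names the test as a 20 m sprint ("standing long jump, and 20m-sprint were identified as measures of lower limb explosive power") and sets three test occasions: "baseline before the experimental intervention, post-test 1 after 4 weeks, and post-test 2 after 8 weeks".

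**The concern.** The sprint is the only one of the three tests with neither a number of attempts nor a scoring rule. The number of attempts is field procedure: a statistical analysis plan written later can choose among recorded times but cannot supply a run that was never timed. The protocol treats attempts and scoring as its own business for the two jumps, so the gap stands out.

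Two things could be at stake. Hand timing is noisy, so one run gives a less precise change score than the best of two or three. And if several runs were made with no rule fixed beforehand, the analyst could take the first, the best or the mean, whichever looked most favourable. A distance of 30 m in the same sentence adds to the impression that the outcome is not properly defined.

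**Working it through.** **Distance.** Mentions of each distance in the protocol:

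| Place | 20 m | 30 m |
|---|---|---|
| Section 1.2 | 1 | 0 |
| Section 4.1, item heading | 1 | 0 |
| Section 4.1, timing sentence | 0 | 1 |
| Section 4.1, cone positions | 1 | 0 |
| Section 4.1, finish instruction | 1 | 0 |
| Table 6, row name and method | 2 | 0 |
| Total | 6 | 1 |

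The course is marked at 0 and 20 m and the finish is the 20 m cone. Nobody could time 30 m on it.

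**Attempts and scoring.**

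| Test | Attempts | Analysed value | Precision |
|---|---|---|---|
| Countermovement jump | 3 | best | not stated |
| Standing long jump | 2 | best | 1 cm |
| 20 m sprint | not stated | not stated | not stated |

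The gap in attempts and scoring is particular to the sprint. The gap in precision is not, since the countermovement jump has none either. Nor is the missing citation: the sources cited for all three tests are absent from the section 6 reference list.

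**Precision of one run.** The protocol gives no sprint variability, so the ratio of s (SD between attempts) to t (SD of true change between dancers) is assumed to be 0.5, 1 or 2. For the shortest of k independent normal times, the variance in units of s² is

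- k = 1: V = 1.000
- k = 2: V = 1 − 1/π = 0.682
- k = 3: V = 1 + √3/(2π) − 9/(4π) = 0.559

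The variance of the change from baseline to week 8 is t² + 2s²V. With t = 1:

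| s/t | k = 1 | k = 2 | k = 3 | ratio 1 to 2 | ratio 1 to 3 |
|---|---|---|---|---|---|
| 0.5 | 1.500 | 1.341 | 1.280 | 1.12 | 1.17 |
| 1 | 3.000 | 2.363 | 2.119 | 1.27 | 1.42 |
| 2 | 9.000 | 6.454 | 5.476 | 1.39 | 1.64 |

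Dividing the 48 dancers by the last column gives 41.0, 33.9 and 29.2. These compare one run with a best of three that the protocol sets for one jump and never for the sprint. They show what extra runs would buy. They are not a loss against the plan.

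**Choosing the score after the fact.** Simulated trials (40,000 per setting, 24 against 24 as an assumed equal split, no true effect, t-test on change, smallest p-value of first, best and mean) rejected in 7.9%, 9.4% and 10.3% of cases with two runs, and in 8.4%, 10.0% and 11.0% with three, for s/t = 0.5, 1 and 2. Any single fixed rule gave 4.8% to 5.3%. The excess therefore needs both repeated runs and selection by result. With one run there is nothing to select. Clustering by location is ignored, so these figures compare scoring rules only.

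**The case for a change.** The strongest case for acting is that singular wording does not settle the matter. The countermovement-jump paragraph also describes a single jump before it specifies three, so the sprint paragraph cannot be read with certainty as one run. The two jump rules differ from each other, so no default carries over. Training takes place at two locations that coincide with the groups, so a number of runs that varied by location could bias the comparison as well as add noise.

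The ambiguity stands, but it does little harm. One run, best of two and best of three are all legitimate ways to score a sprint. Where this protocol wants repeats it says so, which makes one timed run the most natural reading, though not the only one. On bias, if a location kept the same number of runs on all three occasions and timing error stayed the same, the average advantage of taking the best would be the same at each occasion and would cancel from the change score. Bias would need the number to vary over time and differently by location, and nothing in the protocol points to that. Which of several recorded times is analysed is commonly left to the statistical analysis plan, which is not at hand.

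Nor does the precision argument lead to the suggested best-of rule. Under the same model the mean of three has variance 1/3 = 0.333 s² against 0.559 s² for the best of three. Choosing the best would match the jumps, but it would not minimise noise.

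**Conclusion.** The observation is correct, but no change to the plan follows. The 30 m figure is a clerical slip that the surrounding text corrects by itself, and removing it would alter no result. The missing number of runs is a detail that testers and analysts can fill sensibly: followed as written, the text yields a timed 20 m run, which is a sound outcome. The cost of a single run is a variance ratio of 1.17 to 1.64 against a best of three, on assumed variability and against a standard not set for this test. The error rate of 7.9% to 11.0% depends on conduct that no part of the protocol suggests. The effect is confined to one of ten outcomes in Table 6 (three physical tests and seven dance scores), and the protocol does not designate the sprint as primary. The conclusion assumes that the same sprint procedure is used in both groups and on all three occasions. A trial report that gives the number of runs and the time analysed would settle what remains.

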4.2 Latin Dance Performance

Using a video camera, a recorded video of the Cha Cha Gold Medal solo routine is send to the 6 judges, and the pre- and post-tests need to be rated using the same criteria 'the Latin Dance Technical Quality Elements of WDSF2.1 Evaluation System' Objectively assess posture, balance, footwork, preparation-movement-reduction, spinning and rotation, dynamic performance, and line extension (pei, 2023).

Table 5 Scoring Standards for the Qualities of Cha-cha-cha Dancing Skills

Indictors	Very excellent. (10 points)	excellent (8 points)	Above average (6 points)
Posture	Requires the ability to adopt and maintain correct posture during dynamic movement and, with minimal effort, to consciously demonstrate spatial transition postures.	It can drive the entire body to be integrated into the pose, so that the gesture blends with the posture.	The body, in static or dynamic motion, has a well-balanced body structure that includes the head, shoulders, chest, hips, legs, and feet.
Balance	Static: the line of gravity can be reconstructed after dynamic balance movement; Dynamic: can be used naturally and smoothly to generate three-dimensional movement effects, to realize the balance and effect of dance.	Static: can keep its own gravity in the extension line; Dynamic: the use of correct force to achieve dance balance, producing three-dimensional effects	Static: maintains the line of gravity from head to toe; Dynamic: maintaining balance while moving.
Footwork	Control of the spine through the flow of the steps and the transition between centers of gravity to complete the footwork.	Ability to properly utilize foot technique, connecting the necessary foot pressures and hip and body movements.	Ability to properly utilize foot technique.
Preparation-movement-reduction	The ability to perform the full range of motion with a natural and smooth transition from one movement to the next.	It is possible to make the transition from one movement to another during the performance of a complete movement.	Most of the articulated pre-reduction from movement to movement can be accomplished when performing full movements.
Spinning and rotation	Maximize the use of centripetal and centrifugal forces in rotating and turning motions.	It is possible to combine the sagittal plane with the coronal plane when accomplishing rotational and turning movements.	Ability to combine the sagittal and coronal planes most of the time when completing rotational and turning maneuvers
Dynamic performance	Precise use and maximization of power generation in dance movements.	Precise use of power in dance movements	Precise application of power in most dance movements
Line extension	Maintains the lines and extensions of all body parts in both static and dynamic situations.	Maintains most body lines and extensions in both static and dynamic situations.	Maintains a portion of the body line and extends the line in both static and dynamic situations.

Table 6 Outcome Measurement Information

Test Name	Outcome Measure	Measure Method	Instrument	Unit	Suggestions
Explosive power	Countermovement jumps	Recorded maximum altitude	Smart jump mats, iPad	Centimeters (cm)	
	Standing long jumps	Measure the distance of the standing long jump with a measuring tape.	Measuring tape	Centimeters (cm)	
	20m-sprint	Use a stopwatch to record the duration of the participants' 20 m sprint.	Stopwatch	Seconds	
Posture	6 Experts	Recording cha-cha-cha solo gold medal moves, expert scoring	M120 high-speed camera	scores	
Balance	6 Experts	Recording cha-cha-cha solo gold medal moves, expert scoring	M120 high-speed camera	scores	
Footwork	6 Experts	Recording cha-cha-cha solo gold medal moves, expert scoring	M120 high-speed camera	scores	
Preparation-movement-reduction	6 Experts	Recording cha-cha-cha solo gold medal moves, expert scoring	M120 high-speed camera	scores	
Spinning and rotation	6 Experts	Recording cha-cha-cha solo gold medal moves, expert scoring	M120 high-speed camera	scores	
Dynamic performance	6 Experts	Recording cha-cha-cha solo gold medal moves, expert scoring	M120 high-speed camera	scores	
Line extension	6 Experts	Recording cha-cha-cha solo gold medal moves, expert scoring	M120 high-speed camera	scores	

5 Questionnaire information

This questionnaire adopts a 5-point Likert scale, with 1-5 representing increasing support (1=strongly disagree; 2=disagree; 3=not necessarily; 4=agree; 5=strongly agree). Please score the intervention program. If there is other content, you can add them and indicate the name. After reading the questionnaire, please rate the following aspects and tick "√" on the corresponding rating scale.

Table 7 Expert Evaluation Form for Outcome Measurement

6 References

